Duration of Participation	
Stage 1 - Adult Cohort: Each subject will participate in the trial for approximately 30 days from the time the subject signs the Informed Consent Form (ICF) through the final contact. Each subject will receive a single dose of the study vaccine on Day 1. After vaccination, each subject will be followed for 14 days for adverse experiences (AEs). Serious AEs (SAEs) will be collected from the time the consent is signed through completion of the subject's participation in the study (i.e., 30 days postvaccination). Blood samples will be collected prior to vaccination and 30 days postvaccination.

	Stage 2 - Infant Cohort: Each subject will participate in the trial for approximately 11 to 14 months from the time the parent/legal guardian signs the ICF through the final contact. Each subject will receive 4 doses of the study vaccine given at 2, 4, 6, and 12 to 15 months of age. After each vaccination, the study subject will be followed for 14 days for AEs. SAEs will be collected from the time the consent form is signed through 30 days postdose 4 (PD4) and/or completion of the subject's participation in the study. Blood samples will be collected 30 days following the 3 rd dose, immediately prior to the 4 th dose, and 30 days following the 4 th dose.
Randomization Ratio	Stage 1 (adult cohort): 1:1:1:1 Stage 2 (infant cohort): 1:1:1:1:1

A list of abbreviations used in this document can be found in Section 12.5.

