3.3 Other Objectives (Exploratory Objectives)

Stage 1 - Adults Only

1. To evaluate the serotype-specific IgG GMCs of V114 medium with an alternative carrier protein and V114 high with an alternative carrier protein at 1 month postvaccination.

Stage 2 – Infants Only

1. To evaluate the safety and tolerability profiles following receipt of each dose of V114 medium with an alternative carrier protein and V114 high with an alternative carrier protein when administered as a 4-dose regimen to healthy infants at 2, 4, 6, and 12 to 15 months of age.
2. To evaluate the serotype-specific IgG responses of V114 medium with an alternative carrier protein and V114 high with an alternative carrier protein, and the differences in IgG response rates/GMC ratios between each of these V114 formulations and Prevnar 13™ for the 13 common serotypes at 1 month PD3, pre-dose 4, and 1 month PD4.
 - Serotype-specific IgG responses will be based on the GMCs, the proportion of recipients of V114 with an alternative carrier protein achieving the WHO-accepted threshold value of 0.35 µg/mL using the Pn ECL assay for each V114 formulation, and IgG GMC ratios between each V114 formulation with an alternative carrier protein and Prevnar 13.
3. To evaluate the effects of different pneumococcal polysaccharide/MAPA concentrations and use of an alternative carrier protein on serotype-specific GMCs measured at 1 month PD3 across the different formulations of V114.
4. To describe the proportions of subjects with OPA titer ≥ 8 and OPA geometric mean titers (GMTs) in all vaccination groups for the 13 common and 2 non-common serotypes between V114 and Prevnar 13™ at 1 month PD3, pre-dose 4, and 1 month PD4.

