Streptococcus pneumoniae is a major cause of morbidity and mortality worldwide, and causes the deaths of 0.7 to 1 million children <5 years of age, mostly in developing countries [1]. Starting in 2000, Prevnar™ was introduced into national childhood vaccination schedules in the US, European Union (EU), and several other countries. According to the US pediatric vaccination schedule, the vaccine is administered to infants in a 3-dose infant series (2, 4, and 6 months of age), followed by a fourth dose at age 12 to 15 months. Widespread use of the vaccine has led to a significant reduction in invasive pneumococcal disease (IPD), pneumonia and otitis media caused by the 7 serotypes contained in the vaccine [1]. Use of the vaccine in children has also been shown to lower the prevalence of IPD caused by the vaccine serotypes in the non-vaccinated population via herd protection. Prevnar 13™ was approved in the EU in 2009, the US in 2010, and subsequently in other countries worldwide. The vaccine is licensed globally as Prevnar 13™ and Prevenar 13™, and in this protocol the vaccine will be referred to by the name Prevnar 13™. In 2009 a 10-valent pneumococcal conjugate vaccine, Synflorix™ (pneumococcal 10-valent conjugate vaccine [Non-Typeable *Haemophilus influenzae* (NTHi) protein D, diphtheria or tetanus toxoid conjugates], GlaxoSmithKline Biologicals s.a., Rixensart, Belgium) was licensed in Europe and other countries worldwide. Synflorix™ contains the serotypes contained in Prevnar™ conjugated to 3 different carrier proteins, plus 3 additional capsular polysaccharide conjugates (serotypes 1, 5, and 7F). This vaccine is not licensed in the US.

Despite these significant advances, serotype replacement remains a concern as new serotypes begin to fill the niche created by the suppression of nasopharyngeal colonization of vaccine serotypes. In particular, serotypes 22F and 33F, the 2 additional serotypes contained in V114 which are not contained in Prevnar 13™, contributed to approximately 1.3% of overall IPD in children under 5 years of age in the US in 1998 [2], but have now been estimated to represent 22.7% of IPD cases in this age group in 2011 (PPD US CDC, personal communication). This phenomenon of serotype replacement substantiates the need for the development of more broadly-based pneumococcal conjugate vaccines and the search for antigens, such as proteins, that are commonly shared among all pneumococcal serotypes.

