4.2.3 Rationale for Endpoints

4.2.3.1 Immunogenicity Endpoints

Adult Cohort (Stage 1)

For the adult cohort, serum will be collected at 2 pre-specified time points during the trial:

- 1) Prevaccination
- 2) Approximately 30 days postvaccination

Sera will be used for the following measurements in adults:

1. The measurement of serotype-specific IgG using Pn ECL assay.
2. Immunogenicity measurements for the development and validation of future pneumococcal assays.
3. If there are remaining sera after IgG testing, and development of future pneumococcal assays, the leftover sera may be used for Future Biomedical Research (FBR), (Section 4.2.3.3) providing the FBR Informed Consent Form (ICF) has been signed.

In this study, immunogenicity objectives for the adult cohort are not tested as primary objectives; they are evaluated as secondary and exploratory objectives.

Infant Cohort (Stage 2 - Parts I and II)

For the infant cohorts, serum will be collected at 3 pre-specified time points during the trial:

- 1) Approximately 30 days PD3
- 2) Pre-dose 4
- 3) Approximately 30 days PD4

Sera will be used for the following measurements:

1. IgG responses measured using the Pn ECL assay for the study objectives.
2. Functional antibody activity, OPA, will be measured using the MOPA-4 assay in the first 50% of infant subjects who have sufficient serum volume at PD3 to perform both the PnECL and MOPA-4 assays.
3. Immunogenicity measurements for the development and validation of future pneumococcal assays.

4. If there are remaining sera after IgG testing, OPA testing, and development of future pneumococcal assays, the leftover sera may be used for Future Biomedical Research (FBR), (Section 4.2.3.3) providing the FBR Informed Consent Form (ICF) has been signed.

A primary immunogenicity objective is to summarize the antibody response induced by V114 medium, V114 high, and Prevnar 13TM, based on the serotype-specific IgG GMCs measured by Pn ECL assay at 1 month following receipt of the third dose of the study vaccine.

A secondary immunogenicity objective of the study is to summarize the proportion of subjects meeting the serotype-specific threshold value of ≥ 0.35 $\mu\text{g}/\text{mL}$ by Pn ECL assay at 1 month following receipt of the third dose of the study vaccine.

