Serum samples (approximately 40 mL) collected on Day 1 prior to vaccination and on Day 30 postvaccination will be used to measure vaccine-induced immune responses (IgG) to the 15 serotypes contained in V114. These serum samples will be assayed using the Meso-Scale Discovery MSD Pn ECL assay, which was developed by Merck & Co., Inc. for the measurement of pneumococcal capsular polysaccharide IgG antibodies. After completion of protocol-specified immunogenicity assays, leftover sera may be used for the development of future pneumococcal assays. Any remaining sample will then be retained for future biomedical research providing the future biomedical research (FBR) consent has been signed.

Stage 2: Infant Cohort

Subjects will have blood drawn (approximately 4-5 mL) at 3 time points: (1) Day 30 following the third study vaccination (PD3), (2) immediately prior to administration of the fourth study vaccination, and (3) Day 30 following the fourth study vaccination (PD4). Sera

will be used to measure vaccine-induced immune responses (IgG and opsonophagocytic killing activity [OPA]) to all 15 vaccine serotypes included in V114. These serum samples will be assayed using the Meso-Scale Discovery MSD Pn ECL assay, which was developed by Merck & Co., Inc. for the measurement of pneumococcal capsular polysaccharide IgG antibodies. Serum samples will also be assayed using a 4-Fold Multiplex Opsonophagocytic Assay which Merck has developed and implemented in collaboration with [REDACTED]

[REDACTED] from the University of Alabama. If a serum sample does not have enough volume for both the IgG and OPA testing, the IgG testing will take priority. OPA will be evaluated in approximately 50% of subjects with sufficient PD3 sera available to perform both the PnECL and the OPA testing on all 15 serotypes in V114. PD4 OPAs will be conducted for all of the subjects who had PD3 OPAs performed and for which there is sufficient serum. Leftover sera may also be used for the development of future pneumococcal assays. Any remaining sera will be retained for future biomedical research providing the future biomedical research (FBR) consent has been signed.

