8.4.1 Immunogenicity Endpoints

Adult Stage

For the adult stage of the study, there are no primary immunogenicity endpoints. The secondary immunogenicity endpoints are the serotype-specific IgG GMCs and fold-rises from baseline as measured in the Pn ECL assay at 1 month postvaccination for the 15 serotypes in V114.

Infant Stage

For the infant stage of the study, the primary immunogenicity endpoints are the serotype-specific IgG GMCs as measured in the Pn ECL assay at 1 month PD3 for the 15 serotypes in V114 and 13 serotypes in Prevnar 13TM.

The secondary immunogenicity endpoints include (1) the proportion of subjects achieving IgG concentrations $\geq 0.35\mu\text{g/mL}$ at 1 month PD3, pre-dose 4, and 1 month PD4, and (2) the GMCs at pre-dose 4 and 1 month PD4 for the 15 serotypes in V114 and 13 serotypes in Prevnar 13TM.

The exploratory immunogenicity endpoints include the proportion of subjects with OPA titer ≥ 8 and OPA GMTs at 1 month PD3, pre-dose 4, and 1 month PD4 for the 15 serotypes in V114 and 13 serotypes in Prevnar 13TM.

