8.6 Statistical Methods

8.6.1 Statistical Methods for Efficacy Analyses

This section describes the statistical methods that address the primary and secondary objectives. Methods related to exploratory objectives will be described in the supplemental SAP.

Analysis of the immunogenicity data from the infant stage of the study will be based on the combined data from Stage 2 Part I and Stage 2 Part II.

To address the primary infant immunogenicity objective #2, GMCs at 1 month PD3 along with two-sided 95% CIs will be computed for the 15 serotypes in V114 for V114 medium, V114 high, and 13 serotypes in Prevnar 13TM. Point estimates of GMCs are the exponentiated estimates of the mean log_e concentrations. The confidence intervals for GMCs are the exponentiated confidence intervals for the mean log_e concentrations, based on 1-sample t-distributions. Additionally, GMC ratios (V114/Prevnar 13TM) along with two-sided 95% CIs will be computed for each of V114 medium and V114 high relative to Prevnar 13TM for the 13 common serotypes. The CI for the ratio will be calculated using a 2-sample t-test approach based on the natural logarithm of the ratio.

To address the secondary infant immunogenicity objective #1, the proportion of subjects achieving the serotype-specific threshold value of $\geq 0.35\mu\text{g}/\text{mL}$ for the 15 serotypes at 1 month PD3 along with the 95% CI will be calculated for V114 medium, V114 high, and the 13 serotypes in Prevnar 13TM. The one-sample two-sided CIs will be computed using the exact CI method for a single binomial proportion given in Collett [7]. Additionally, the

difference (V114 minus Prevnar 13TM) in the proportion of subjects achieving an IgG concentration $\geq 0.35\mu\text{g/mL}$ along with two-sided 95% CIs will be computed for each of V114 medium and V114 high relative to Prevnar 13TM for the 13 serotypes in common. The CI for the difference will be computed using the method of Miettinen and Nurminen [8].

The additional secondary infant immunogenicity objective (#2) as well as the secondary adult immunogenicity objective #1 will utilize similar statistical methods as those outlined above.

Reverse cumulative distribution functions for both IgG and OPA levels at PD3 and PD4 will be graphically displayed by serotype in the CSR.

Table 4 summarizes the key immunogenicity analyses.

Table 4 Analysis Strategy for Key Immunogenicity Variables

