Adult and small infant cohort	
Adult GMC ratios for each of the 15 serotypes contained in V114.Adult GMCs at baseline and 1 month postvaccination, GMFR and % of subjects who achieved at least 4-fold rise at 1 month postvaccination for each of the 15 serotypes contained in V114.Adult percentage of subjects with any AE, a vaccine related AE, a serious AE, an AE which is both vaccine-related and serious, and who discontinued due to an AE.Small infant cohort PD3 GMCs and GMC ratios, for the 15 serotypes contained in V114.Small infant cohort PD3 proportion of subjects of subjects achieving concentrations $\geq 0.35 \mu\text{g/mL}$ and differences, for each of the 15 serotypes in V114.Percentage of infants in the small cohort with any AE, a vaccine related AE, a serious AE, an AE which is both vaccine-related and serious, and who discontinued due to an AE after each vaccination.	~100% of the adult cohort and small cohort of infants have completed safety follow-up (postvaccination for adult cohort and postdose 3 for small infant cohort) and ~100% of the immunogenicity results (IgG responses) for adult (postvaccination) and small infant (postdose 3) cohorts are available.	Inform scientific decisions for future studies

Interim Analysis	Key Endpoints of Interim Analysis	Timing of Interim Analysis	Purpose of Interim Analysis
All Infant Cohorts	
• Infant PD3 GMCs and ratios, for the 15 serotypes contained in V114.• Infant PD3 proportion of subjects achieving IgG concentrations $\geq 0.35 \mu\text{g/mL}$ and differences, for each of the 15 serotypes in V114.• Infant PD3 percentage of subjects with any AE, a vaccine related AE, a serious AE, an AE which is both vaccine-related and serious, and who discontinued due to an AE.	~100% of PD3 immunogenicity results (IgG responses) for all infants (small and large cohorts) are available.	Inform scientific decisions for future studies

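### The final infant IgG analysis gives no background estimate for serotypes 22F and 33F, because the Prevnar 13 arm is summarised for 13 serotypes only

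*Combined protocol and SAP*

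**What the plan says.** **Sampling.** Section 4.2.3.1 states: "For the infant cohorts, serum will be collected at 3 pre-specified time points during the trial". These are PD3, pre-dose 4 and PD4. The trial summary agrees ("Blood samples will be collected 30 days following the 3 rd dose, immediately prior to the 4 th dose", then 30 days after dose 4). No infant is bled before dose 1.

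**Assays.** Section 7.1.3.1 has infant sera measured for IgG and OPA responses "to all 15 vaccine serotypes included in V114" and makes no exception for the Prevnar 13 arm. If serum is short, IgG takes priority, and OPA is run in about half of infants with enough PD3 serum. In the IgG assay, 22F and 33F share a multiplex group with five serotypes that are in Prevnar 13.

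**Final analysis.** In 8.6.1, PD3 GMCs are "computed for the 15 serotypes in V114 for V114 medium, V114 high, and 13 serotypes in Prevnar 13TM". Sections 8.1 and 8.4.1 and Table 4 use the same 15/13 split for GMCs and for the proportion at or above 0.35 µg/mL. Ratios and differences against Prevnar 13 cover the 13 common serotypes.

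**Elsewhere in the plan.** Table 6 (8.7) lists, for the first interim, "Small infant cohort PD3 GMCs and GMC ratios, for the 15 serotypes contained in V114", with differences in response rate for the same 15; the second interim does this for all infants. Exploratory objective 4 (3.3) describes OPA "in all vaccination groups for the 13 common and 2 non-common serotypes". Section 8.4.1, in the sentence that begins "The exploratory immunogenicity endpoints include the proportion of subjects with OPA titer", limits Prevnar 13 to 13 serotypes.

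**The concern.** Section 4.3 gives the added benefit of V114 over Prevnar 13 as coverage of 22F and 33F. For the common serotypes, an infant IgG result can be read against a randomised comparator. For the two added serotypes, the final IgG tables offer neither a comparator nor a pre-vaccination value, so they cannot separate vaccine-induced antibody from maternal antibody, natural exposure or assay background.

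Exposure is plausible. Section 4.1.1 says that the two serotypes together made up about 1.3% of invasive disease in US children under 5 in 1998, "but have now been estimated to represent 22.7% of IPD cases in this age group in 2011". That is a share of disease cases; it does not measure antibody prevalence or carriage.

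The Prevnar 13 arm is randomised, concurrent, assayed for both serotypes and not immunised against either. It is the natural measure of background. The final IgG tables do not use it for this purpose.

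**Working it through.** **1. The passages side by side (22F and 33F in the Prevnar 13 arm)**

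| Place | Measure and time | Prevnar 13 shown or compared for 22F/33F? |
|---|---|---|
| 8.6.1, Table 4 | IgG GMC and ratio; PD3, pre-dose 4, PD4 | No |
| 8.6.1, Table 4 | IgG proportion ≥0.35 and difference; same times | No |
| 8.6.1 | Reverse cumulative curves, IgG and OPA; PD3, PD4 | Arms not stated |
| 8.7, Table 6 | IgG ratio and difference at interim; PD3 only | 15 serotypes, comparator not named |
| 3.3, objective 4 | OPA; PD3, pre-dose 4, PD4 | Yes, all groups |
| 8.4.1 | OPA; same times | No (13 serotypes) |

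No row gives an IgG contrast with Prevnar 13 for 22F or 33F at pre-dose 4 or PD4.

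**2. The plan's own figure.** Inputs from 8.9: 45 evaluable per arm at PD3, SD of ln concentration 1.0, 2-fold difference, one-sided alpha 0.05. Noncentrality = ln 2 / (1.0 × √(2/45)) = 0.693/0.2108 = 3.29, with 88 degrees of freedom and critical t 1.662. Power is 94.7%, as stated. The point disputes no figure in the plan.

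**3. Precision of an added 22F or 33F GMC ratio.** By the planned two-sample t method, the 95% limits are the estimate multiplied and divided by exp(t × SD × √(2/45)), with t = 1.987.

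- SD 0.8: exp(0.335) = 1.40
- SD 1.0: exp(0.419) = 1.52
- SD 1.4: exp(0.586) = 1.80

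This equals the precision for a common serotype with the same SD. Section 8.9 does not say that its SDs apply to an arm given no 22F or 33F antigen, so applying the 0.8 to 1.4 range here is an assumption.

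**4. What the missing contrast would show.** All counts here are assumptions. Take 27/45 = 60% of a V114 arm at or above 0.35 µg/mL. The planned within-arm output is 60%, exact 95% CI 44% to 74%, whatever the background. The difference by the Miettinen-Nurminen method (the plan's own) would be:

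| Assumed Prevnar 13 count | Rate | Difference, points (95% CI) |
|---|---|---|
| 2/45 | 4% | 56 (39 to 70) |
| 9/45 | 20% | 40 (20 to 57) |
| 18/45 | 40% | 20 (−1 to 39) |

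The plan states 45 evaluable for PD3 only. Fewer are likely at pre-dose 4, because infants who meet the rescue criterion at PD3 leave the study with no further immunogenicity blood draw (5.6, 5.8).

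**5. Why pre-dose 4 stands out.** Dose 3 is given from 6 months to a day before 7 months, and dose 4 from 12 months to a day before 16 months. The gap runs from about 12 − 7 = 5 to 16 − 6 = 10 months, so there is time for vaccine antibody to wane and exposure to accumulate. Table 6 does not reach this time point.

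**The case against.** **The trial does not lack a control for these serotypes altogether.** A reader might infer that it does, and the documents do not support that. Exploratory objective 4 covers both serotypes by OPA in every group. Table 6 lists 15-serotype PD3 ratios and differences, at the second interim on nearly all PD3 data. The reverse cumulative curves exclude no arm, and methods for the exploratory objectives are left to a supplemental SAP. All of this stands, and it limits the point to the final IgG analysis. It does not close the gap: OPA covers about half of infants and 8.4.1 contradicts the objective; Table 6 is interim and PD3 only; the curves omit pre-dose 4.

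**Table 6 cuts both ways.** Its adult ratios can only compare V114 arms. If the infant ratios are against Prevnar 13, PD3 is covered at interim and Table 6 differs from 8.6.1. If they are between V114 arms, there is no conflict, but also no background estimate. The first reading is the more natural, since the plan elsewhere defines infant ratios against Prevnar 13, but it is not certain. The comparator has to be stated either way.

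**The IgG analysis follows its objectives.** Primary objective 2 and secondary objectives 1 and 2 limit contrasts to the common serotypes, and no test or decision rule depends on 22F or 33F. This is correct. The change is an inexpensive improvement to an estimation study; it does not correct a broken analysis.

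**The missing baseline is only context.** Adults have a baseline and fold-rises. In infants, a sample at 42 to 90 days could carry maternal antibody, and the fix does not ask for one.

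**The counts are invented.** They are, and only the highest assumed background gives an interval that includes zero.

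**Conclusion.** The point holds for the final infant IgG analysis. There, 22F and 33F are reported as within-arm V114 values with no background estimate, although the Prevnar 13 sera that would supply one are to be assayed. The gap is clearest at pre-dose 4 and PD4; at PD3 it depends on the comparator that Table 6 intends. Separately, 8.4.1 and exploratory objective 4 disagree on OPA for the Prevnar 13 arm.

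The size cannot be fixed from the documents, which give no background rate. Under the assumed counts, one planned result of 60% is compatible with differences from 20 to 56 points. It would go too far to say that V114's 22F and 33F responses are likely to be mostly background, or that the disease share in 4.1.1 shows this.

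**What to change.** - In 8.4.1, 8.6.1 and Table 4 (and the summary in 8.1), summarise the Prevnar 13 arm for all 15 serotypes.
- For 22F and 33F, add the V114/Prevnar 13 GMC ratio and the difference in the proportion at or above 0.35 µg/mL (V114 minus Prevnar 13), with 95% CIs by the methods already planned, at PD3, pre-dose 4 and PD4. Label them descriptively as response over background. Note that the later time points exclude infants discontinued after PD3.
- In Table 6, name the comparator for the infant ratios and differences.
- Align the OPA endpoint in 8.4.1 with exploratory objective 4, and note that OPA has about half the sample.

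The cost is SAP wording and a few table rows, with no added infants, blood draws or assays beyond those planned. Because the study is one of estimation, the added rows need no multiplicity adjustment. Under 8.0, the change can go into the supplemental SAP before unblinding, which avoids a post hoc label.
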